Secondary outcomes will include: pre-analgesia pain score (P_o), post-operative pain score (P_{20}), patient intolerance to the procedure, postoperative voiding trial results (pass/fail), and post void residual (PVR) results at 2 week follow-up (measured in ml, pass/fail), and diagnosis of urinary tract infection (accepted clinical definition of acute cystitis or a positive urine culture) at 2 week follow-up. PVRs < 200ml at 2 week follow-up will be considered passing result [31].

Participants will also rate their level of satisfaction with pain control immediately after the procedure using a simple Likert scale. This will be a 4-level scale ranging from 'not at all satisfied,' 'slightly satisfied,' 'mostly satisfied,' and 'very much satisfied.'

Expected Results

Investigators believe that participants randomized to the B&O suppository group will experience less bladder pain (average pain) during the BoNT injection procedure than those that were assigned to the placebo group.

Study Type and Design

This study is a randomized, pilot trial. Clinical investigators and participants will be blinded to the randomization groups. Participants, whom have elected to receive BoNT injection therapy, will be randomized to receive either a placebo or B&O suppository prior to the procedure. Pain will be assessed prior to the procedure, during the procedure, and after the procedure.

Sample size

Sample size is calculated assuming the group receiving the B&O suppository reports an average intra-procedural pain (P_{10}) score of 4.5, and assuming the control group (placebo) reports an average intra-procedural pain (P_{10}) score of 8. The assumed standard deviation is 3. Based on a power of 0.8, the required sample size per randomization group is 13. The total sample size required to achieve a power of 0.8 for this pilot trial would be 26 (13 per group).

Randomization

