Eligible participants will be assigned with equal probability to one of two treatment groups: belladonna and opiate (B&O) suppository and inactive placebo suppository. Block randomization will be utilized to maintain balance between study group sizes over time and to enhance blinding of the clinical investigators; a repeated run of placebo or active suppositories may lead to an anticipatory bias effect on subsequent participants. An online randomized block generator will be utilized. Block size will be randomized and will not be revealed to clinical investigators. As the proposed study is double-blinded, selection bias is unlikely.

Study drug suppositories will be randomized in sequential pill canisters. Aside from standard indications to do otherwise, treatment allocation will remain concealed until enrollment and follow-up visits have been completed.

Working with the compounding pharmacy, an unblinded data coordinator will label, and track, the active and placebo drug assignments. Once the patient has consented to participate in the study, the Principal Investigator will assign the participant sequentially, and will notify the data coordinator and compounding pharmacy. Based on a sequential numbering system, the participant will be randomized to receive either the B&O suppository or the inactive placebo suppository based on the block assignment. The Principal Investigator will complete an authentic prescription in order to comply with all Drug Enforcement Administration (DEA) requirements for securing Schedule 2

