narcotics. The prescription will be provided to the compounding pharmacy, which will fill the prescription based on the pre-determined randomization scheme. The compounding pharmacy will document and deliver the pill canister matching the participant's ID number, to the clinic and provide it to the Principal Investigator to store in a locked medicinal refrigerator in a locked room until the day of the procedure. Prior to administering the suppository to the patient during the procedure, the Principal Investigator will open the pill canister and document the pill canister number and the number labeled on the suppository in the patient's medical record, and study documents. If unveiling the randomization for a participant is required, the Principal Investigator can call the data coordinator or the compounding pharmacy, and the coordinator or the lead pharmacist will reveal the participant's randomization assignment over the phone. Monthly meetings will be conducted to audit the enrollment and to ensure randomization procedures are conducted appropriately.

Statistical Analysis

Preoperative demographic variables including age, race, parity, body mass index (kg/m^2), menopausal status, smoking status, medical comorbidities, and indication for BoNT treatment (OAB vs. NDO) will be compared between active and placebo patients. Continuous variables will be compared using Student t-tests. Categorical variables will be described as frequency data (proportions & percentages) and compared using Chi-square or Fisher's exact test (when expected values in any cell are less than 5). Ordinal variables will be compared using Wilcoxon Rank Sum tests.

An intent-to-treat analysis approach will be used. Results for the active group versus the control group will be compared with paired t-tests if the data are normally distributed and with Mann-Whitney tests if the data are skewed. Regression modeling will be used to analyze the relationship between our primary outcome with the following predictor variables; active vs. placebo, indication for BoNT injection (OAB vs. NDO), demographic variables, and pain scores (before-during-after procedure). Interactions between variables will be assessed and, if significant, included in the model.

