The active suppositories and placebo suppositories will be compounded to be physically identical, and will be provided directly to the Principal Investigator located at Wichita Women's Pelvic Surgery Center at Associates in Women's Health, by the compounding pharmacy. The Principal Investigator will not know the identity of the suppositories. The data coordinator will maintain a master tracking list of the suppository with an inventory or ID number provided by the pharmacy as to which ID numbers are placebos and which are the B&O suppositories. The data coordinator will provide the randomization scheme to the pharmacy, who will fill each individual prescription based on the order the patient is consented into the study (using the participant's ID number), and will place the individual suppository into a blinded pill canister. The Principal Investigator will call the data coordinator and the lead pharmacist at the compounding pharmacy when a patient has consented and will undergo the procedure. The pharmacist associated with the compounding pharmacy will hand deliver the envelope to the clinic, and document the pill canister being delivered. The data coordinator will meet the pharmacist at the clinic to audit the container, and to confirm the appropriate container is provided to the Principal Investigator. The "unblinded" label containing the actual medication provided to the patient, including the patient name, date of birth, address, and phone number will be concealed in an envelope and carried separately from the pill canister, however, in order to comply with DEA guidelines, both will be hand delivered to the clinic. The envelope with the identity of the suppository will be in a secure container under lock and key, and will only be accessible to the data coordinator. The label will be stored with the participant's study records, and not revealed to the Principal Investigator.

All suppositories will be stored in a locked refrigerator that will be kept in a locked office. The temperature will be monitored regularly for quality assurance. The Principal Investigator will administer the suppository to the participant prior to the BoNT procedure, and will document in the participant's medical record and study documents which pill number was administered to the participant. The data coordinator will monitor

and monthly audit logs to ensure randomization assignments are adhered to during the course of the study.

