Assemble project staff, create study protocol, submit for IRB approval and study funding													
Submit project for IRB approval and funding													
Receive IRB Approval			X										
Train study team and support staff													
Recruit patients from local providers offices													
Enroll patients and collect data													
Team meetings to discuss research plan, data quality, and progress on objectives													
Conduct preliminary analysis													
Review findings with team													
IRB Continuing Review													
	Academic Year 2016 - 2017												
Finalize data analysis and conclusions													
Draft abstract and submit to regional/national conferences		X											
Disseminate preliminary findings at regional/national conferences				X						X			
Draft manuscript													
Submit manuscript for publication							X						

Budget and Justification

Investigators will be requesting funding to cover costs related to the study and registration for the Principal Investigator and the Resident Investigator to present the findings of this study at the 2016 American Urogynecologic Society Annual Meeting. A detailed budget is provided below.

Personnel Costs: **\$0.00**
[name], MD, Principal Investigator (PI), will be responsible for managing and providing direction on all aspects of the project, ensuring that the budget and timetable targets are met, and providing direction to the other research personnel. Specifically he will facilitate communication between members of study team, and oversee conduct of the study, ensure all requirements for the Institutional Review Board are met, and contribute to reports, and dissemination. [name] will be performing the clinical procedures associated with this study, perform the data analysis and create reports, and disseminate results at national meetings.

[name], PGY-3, Co-investigator, will be responsible for managing and providing direction on all aspects of the project, ensuring that the budget and timetable targets are met, support Institutional Review Board approval/revisions, and providing direction to the other research personnel. Specifically she will facilitate communication between members of study team, and oversee conduct of the study personnel, perform study procedures, assist with data analysis, and create reports, and dissemination at national meetings.

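### Concealment is guaranteed only until follow-up visits end; it is not extended through data cleaning, exclusions, outcome classification or fixing of the analysis, which the operating investigator performs

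*Combined protocol and SAP*

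**What the plan says.** **Blinding and its end.** Under Study Type and Design, "Clinical investigators and participants will be blinded to the randomization groups". No analyst or statistician is listed as masked. The Randomization section gives the only end point for concealment: "treatment allocation will remain concealed until enrollment and follow-up visits have been completed", with an exception worded "Aside from standard indications to do otherwise" that is not defined further. In the same section, "an unblinded data coordinator will label, and track, the active and placebo drug assignments". Under Origin, Tracking, and Dispensing of Suppositories, "The label will be stored with the participant's study records, and not revealed to the Principal Investigator"; no end date is given.

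**Who analyses.** Budget and Justification says of the Principal Investigator that he "will be performing the clinical procedures associated with this study, perform the data analysis and create reports". The co-investigator and study personnel assist with analysis, and the study personnel also assist with data cleaning. Cleaning is not placed before or after decoding.

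**What is left to judgement.** Under Statistical Analysis, groups are compared by a t-test "if the data are normally distributed and with Mann-Whitney tests if the data are skewed", with no criterion for deciding which applies. Interactions are kept when significant, confounders when estimates move by more than 20%, and continuous variables may be categorised on fit statistics. Intolerance to the procedure is a secondary outcome without a definition (Outcomes). Under Cessation Rules/Termination of Study, the Principal Investigator may remove patients who do not meet study requirements.

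**The concern.** Blinding during treatment protects the pain scores as they are given and recorded. It does not protect what happens to them afterwards: which records are queried or set aside, who counts as intolerant, whether the data are called skewed, and which covariates enter the model. If the person making those decisions knows the arms, they can lean towards the expected answer without anyone intending it.

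The expectation here is explicit. Expected Results records the investigators' belief that the active group will have less pain. Risks to Subjects and Alternatives to Participation describe the active suppository as this investigator's routine care. At stake is whether the double-blind claim, on which the protocol relies for rigor, reaches as far as the reported result.

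**Working it through.** **1. Promise set against the tasks that need it.**

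- Enrollment and visits: concealment promised (Randomization).
- Closing queries and cleaning: a staff task in Budget and Justification, with no link to decoding.
- Removing patients: discretionary, with no masked sign-off (Cessation Rules/Termination of Study).
- Classifying intolerance: undefined and untimed (Outcomes).
- Choosing test, covariates, interactions and categories: driven by the data, with no masking (Statistical Analysis).
- Interim analysis at one year if data collection is incomplete: no masking rule (Statistical Analysis), and the investigators review interim efficacy themselves in place of a DSMB (Study Monitoring).

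Only the first item is covered by the promise. A database lock, blind data review or coded-arm analysis appears nowhere.

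**2. The plan's own figure.** Sample size assumes means of 8 and 4.5 and an SD of 3, so the standardised difference is 3.5/3 = 1.167. A two-sided two-sample t-test at 0.05 with 80% power needs 12.57 per arm, rounded up to 13, or 26 in total; power at 13 is 0.814. The figure reproduces, and nothing proposed here alters it.

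**3. Do the flexible rules inflate type I error?** The simulation assumed no true effect, 13 per arm, normal outcome with SD 3, five candidate covariates (two split at the median) generated with correlation 0 or 0.3 with the outcome, and 10,000 trials. The covariates and correlations are assumptions, not taken from the documents. Near 0.05 the Monte Carlo standard error is √(0.05 × 0.95/10,000) = 0.002.

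| Analysis | Correlation 0 | Correlation 0.3 |
|---|---|---|
| One fixed t-test | 0.048 | 0.052 |
| Normality test decides t or Mann-Whitney | 0.050 | 0.053 |
| 20% change-in-estimate rule | 0.062 | 0.053 |
| Smaller p of t and Mann-Whitney | 0.056 | 0.059 |
| Best of t, Mann-Whitney, 20%-rule and single-covariate models | 0.087 | 0.117 |

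The second and third rows mechanise rules the plan states; the last two are departures from it. Each two-sided p-value is unchanged if the arm labels are swapped, so an analyst seeing only A and B could run the same search and reach the same last row. The table measures freedom of analysis, not knowledge of the arms.

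**4. What one discretionary exclusion can move.** Dropping a patient who lies d from the arm mean shifts that mean by d/(n − 1). With d equal to the plan's SD of 3 (stated for the mid-procedure score) and n = 13, the shift is 3/12 = 0.25 NRS points. The standard error of the difference is 3 × √(2/13) = 1.18, so one such exclusion moves the comparison by 0.25/1.18 = 0.21 standard errors.

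**The case against.** The strongest reply is that concealment to the end of visits is a minimum. A reader might infer that the allocation is opened the moment the last visit ends, before cleaning, and that all the analysis choices follow with the arms known. The documents do not support that sequence. They give no time of decoding and do not order cleaning relative to it, and the label withheld from the Principal Investigator has no end date. What stands against the reply is that the label provision does not mention analysis, so it does not clearly extend the blind to that stage.

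A reader might also attach a false-positive rate of around 12% to the missing masking. That too fails: such a rate requires free selection among p-values, which the plan does not prescribe and coded labels would not prevent.

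Other safeguards count. The primary outcome is subtraction of two patient-reported scores taken on the procedure day under blinding. Baseline completeness is verified before randomization, safety and data are reviewed monthly, responsibility for data quality is assigned, and analysis is by intention to treat. These leave little to adjudicate in the primary score itself. They do not settle removals, intolerance or model choice. The section that allows removal also leaves data collected before cessation on hold at the investigators' discretion, without reconciling this with intention to treat.

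Finally, prespecifying the analysis would make part of the masking redundant. That is true for test and model choice, but not for cleaning, exclusions and classification.

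**Conclusion.** The gap is real and modest. Concealment is guaranteed to the end of follow-up and no further, while the operating investigator, who has a stated expectation of benefit, is named to analyse the data, may remove patients, and works under rules that leave several choices to the data. No passage closes that gap.

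Its effect on the result cannot be quantified from the documents. The test-choice and 20% rules, simulated alone, keep type I error at about 5% to 6% on the stated assumptions. A single exclusion one SD from its arm mean moves the comparison by about a fifth of a standard error, using the plan's SD as a stand-in for that of the change score. The conclusion rests on the absence of any lock or masking provision in the protocol, not on evidence that arms would be opened early or choices misused. Because the remedy is nearly free, the change should be made even in a pilot of 26.

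**What to change.** Replace the concealment sentence in Randomization. Apart from emergency unblinding, allocation stays closed to everyone except the data coordinator and the pharmacy until all queries are closed, exclusions and outcome classifications (including a written definition of intolerance) are signed off, and the database is locked. Say how the one-year interim analysis fits with this.

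In Statistical Analysis, fix the primary test and a named covariate list in writing before any arm-labelled data are seen, looking at pooled data only if needed. This replaces choosing the primary model by the 20% change-in-estimate and significant-interaction rules, which cannot be applied to the treatment effect while arms are hidden. Then run the primary analysis under A/B labels supplied by the coordinator, and decode afterwards. The order matters, because A/B labels alone do not stop selection on significance.

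The cost is a few sentences of protocol text and a short delay before decoding. No staff are added, since the coordinator already holds the list, and the sample size stays at 26.

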valid and reliable measure of pain intensity [30]. The primary outcome of our study will be determined by the patient experience objectified with the NRS. The overall goal of this study is to improve the patient experience with cost-effective evidence-based treatment.

Research Plan and Design

Study Objectives

The primary objective is to determine the effectiveness of B&O suppositories in decreasing bladder injection pain at time of BoNT injection.

Our null hypothesis: Among patients given standard analgesia for BoNT treatment of overactive bladder (OAB), neurogenic detrusor overactivity (NDO), or refractory interstitial cystitis (IC), there is no difference in bladder injection pain scores with the addition of B&O suppository when compared to placebo suppository.

H₀: Mean Δ pain during procedure in active suppository group = mean Δ pain during procedure in placebo suppository group.

Change in pain (*Mean Δ pain*) is considered to be the difference in pain from the baseline pain level after analgesia, and after the first 10 injections.

Outcomes

The primary outcome will be bladder injection pain. Pain will be measured using numeric rating scales (NRS). Participants will score their preoperative baseline pain level when they check into the clinic for their procedure (P_o). Participants will report pain 40 minutes after administration of standard analgesia and suppository (just prior to bladder injection) (P_a). This will allow calibration of our primary outcome for patients with higher levels of baseline pain not related to the procedure (using themselves as controls). They will then be asked to rate bladder pain after the first 10 injections (midpoint of the procedure) intraoperatively (P_{10}). After the procedure is completed, which would be after 20 injections, the patient will again be asked to report their pain (P_{20}).

The operational definition of our primary outcome will be calculated difference in NRS pain score prior to procedure (P_a) and midway through procedure (P_{10}): Δ pain (intraoperative pain score – preoperative pain score).

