Confounding variables will be included in the model if point estimates change by more than 20% with their inclusion. Continuous variables will be assessed for linearity and converted to categorical variables as indicated by model fit statistics (c-statistic, Deviance, Pearson, Hosmer-Lemeshow). Cochran-Armitage and Goodness of Linear Fit tests will be used to evaluate for linear trends between suppository treatment and our primary outcome.

All statistical analyses will be two-sided. P-value of less than 0.05 is considered to be statistically significant. An interim analysis will be performed one year after Institutional Review Board if the study has not completed data collection within one year. Results will not be given to participants.

Participants

Patients will be approached for participation once they have selected BoNT therapy for treatment of overactive bladder (OAB), neurogenic detrusor overactivity (NDO), or refractory interstitial cystitis (IC).

To be included in this study, patients must be 18 years old or older at the time of the informed consent discussion, have met clinical criteria under outside care or during the Principal Investigator's routine standard of care for BoNT injection therapy (failed initial medical management), and there must be no contraindication to BoNT therapy as outlined by drug manufacturer guidelines (Table 1). Patients will have elected to have the BoNT injection therapy prior to being offer enrollment into the study for either OAB, NDO, or IC.

Patients will be excluded for pregnancy, currently nursing a baby, age less than 18 years, or anticipated geographic relocation within the first 3 months following treatment. Patients will be excluded if the patient reports an allergy to morphine, belladonna, or opiates. Patients will also be excluded if participating in another research study. Individuals unable to provide informed consent or to complete two-week follow-up bladder testing (post-void residual) or data collection will also be excluded. Prior to randomization, a data coordinator will verify eligibility and completeness of baseline data.

Participants will be withdrawn or terminated from participating in the study by a clinical investigator if they fail to undergo the BoNT injection procedure and do not reschedule before the conclusion of the study.

[figure not shown]

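### The between-arm comparison is specified as a paired t-test, but the two randomised arms are independent and no pairs are defined

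*Combined protocol and SAP*

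**What the plan says.** The Statistical Analysis section gives the between-arm test as follows: "Results for the active group versus the control group will be compared with paired t-tests if the data are normally distributed". For skewed data it switches to Mann-Whitney. The sentence just before it reads "An intent-to-treat analysis approach will be used".

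Other parts of the document describe a design with two independent groups:

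- **Randomization:** "Eligible participants will be assigned with equal probability to one of two treatment groups". On blocking: "Block size will be randomized and will not be revealed to clinical investigators". No matching rule is given.
- **Study Objectives:** the null hypothesis is that "there is no difference in bladder injection pain scores with the addition of B&O suppository when compared to placebo suppository", written as equality of the two arms' mean changes in pain.
- **Outcomes:** each participant contributes one primary value, P10 − Pa (pain after ten injections minus pain just before injection).
- **Sample size:** 13 per group, 26 in total, for power 0.8.
- **Statistical Analysis, baseline comparisons:** "Continuous variables will be compared using Student t-tests".

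**The concern.** A paired t-test works on differences within pairs. Here no active participant is matched to a placebo participant, there is no crossover, and blocks of random size do not form pairs. An analyst who follows the sentence literally must invent a pairing, and different pairings of the same 26 values give different p-values.

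A within-participant reading does not rescue the wording. Each participant already serves as their own control through the subtraction of Pa. A paired test of Pa against P10 inside one arm would not test the stated null hypothesis, and the sentence explicitly compares active with control.

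There is also a conflict with intent-to-treat. If the arms have unequal numbers of evaluable participants, those without a partner are left out although they have data. Unequal arms are possible: block size is random, and the Participants section withdraws people "if they fail to undergo the BoNT injection procedure and do not reschedule before the conclusion of the study". Those withdrawn have no P10 − Pa under either test, so the extra loss caused by pairing is limited to their unmatched counterparts in the other arm.

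**Working it through.** **Inputs.** Sample size section: means 4.5 and 8 (difference 3.5), SD 3, power 0.8, 13 per group. Statistical Analysis section: two-sided, 0.05. Assumptions made here: correlation 0 between arbitrarily paired participants, and SD 3 applied to P10 − Pa, because the document gives an SD only for the P10 calculation.

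**1. The plan's own figure.** For an independent t-test with n per arm, the standard error is SD × √(2/n), the noncentrality is difference / standard error, and df = 2n − 2.

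- n = 13: SE = 3 × √(2/13) = 1.177; noncentrality 3.5 / 1.177 = 2.974; df 24; critical t 2.064; power **0.814**.
- n = 12: power 0.780.

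So 13 per group is what an independent two-sample t-test requires.

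**2. The test as written.** With unrelated pairs, the SD of the paired difference is 3√2, so the SE is 3√2 / √13 = 1.177 and the noncentrality is again 2.974. The df fall to 12 and the critical t rises to 2.179.

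- 13 pairs: power **0.779**, a loss of 0.814 − 0.779 = 0.035.
- 14 pairs: power 0.814, so 14 per arm would be needed to reach 0.80.

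**3. Unequal evaluable arms.** The splits are illustrative, because the document gives no block sizes or missing-data rate.

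| Evaluable split | Independent test, all data | Paired test |
|---|---|---|
| 13/13 | 0.814 | 0.779 (13 pairs) |
| 14/12 | 0.812 | 0.740 (12 pairs) |
| 13/12 | 0.797 | 0.740 (12 pairs) |

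**4. Sensitivity to the SD of the change score.** At 13/13 with difference 3.5:

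| SD of P10 − Pa | Independent | 13 arbitrary pairs |
|---|---|---|
| 2.5 | 0.928 | 0.905 |
| 3.0 | 0.814 | 0.779 |
| 3.5 | 0.687 | 0.649 |

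The loss from pairing is about 2 to 4 points throughout.

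**5. Type I error** (simulation, 200,000 trials, 13 per arm). Independent test 0.050; pairing fixed without sight of outcomes 0.050. As outer limits, sorting both arms by outcome in the same direction gives 0.53, and sorting them in opposite directions gives 0.006.

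**6. How far the p-value moves on the same data.** For each observed difference, 60 data sets were scaled to SD 3 with 13 per arm, and each was randomly re-paired 5,000 times. The independent p comes from t = difference / 1.177 on 24 df. The paired range is the central 95%, averaged over data sets.

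| Observed difference | t | Independent p | Paired p, central 95% | Pairings below 0.05 |
|---|---|---|---|---|
| 3.5 | 2.97 | 0.0066 | 0.0008 to 0.034 | 99.99% |
| 3.0 | 2.55 | 0.018 | 0.0025 to 0.063 | 89% |
| 2.5 | 2.12 | 0.044 | 0.008 to 0.114 | 44% |

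The 3.0 and 2.5 are illustrative observed results, not figures from the document.

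**7. Disagreement between tests.** With a true difference of 3.5, the Student and arbitrarily paired tests reach different verdicts in 7.2% of simulated trials: 5.3% significant by the independent test only, 1.9% by the paired test only.

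**The case against.** The strongest reply is that this is a one-word slip. The null hypothesis, the per-group sample size and the Mann-Whitney alternative in the same sentence all assume independent arms, and 13 per group is exactly the independent-test answer. A competent analyst would probably run an unpaired test. That is very likely right and limits how serious the point is, but it does not make the written sentence executable.

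It can also be argued that other text covers the comparison. The Student t-test sentence is not itself limited to baseline variables, and the regression includes active versus placebo. However, the Student t-test sentence follows directly from a list of preoperative variables, so a baseline-only reading is the natural one. The regression is not designated as primary. The document does not label the paired t-test as primary either, but that is the test its between-arm sentence names.

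The realistic effect is modest. With a pairing chosen without sight of outcomes, type I error is kept and about 3.5 power points are lost in a self-described pilot. At an observed 3.5 almost every pairing remains significant. The sorted-outcome error rates describe nothing the document proposes, and they should be read only as limits on what an unspecified pairing allows. The unequal splits are illustrative, and at 13/12 even the independent test falls just below 0.80. All of this stands.

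Finally, correcting the test does not confirm that 26 is enough. If the SD of the change score were 3.5, the independent test would have power 0.687. That is a separate question about the sample-size inputs.

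**Conclusion.** The concern holds: the named test does not fit the design and gives no unique p-value. It should be fixed. It is probably a drafting error, and the likely numerical damage is small: power 0.779 instead of 0.814 at the planning values, with type I error intact, provided the pairing ignores outcomes. The greater weakness is an undefined analyst choice that can change the verdict on a borderline result and can drop participants with data from a trial of 26. The power figures rest on the planning difference of 3.5, SD 3 carried over to P10 − Pa, and zero correlation within arbitrary pairs. The borderline results and unequal splits are illustrations.

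**What to change.** In the Statistical Analysis section, replace the paired t-tests with an independent two-sample t-test (Student or Welch) on P10 − Pa, or with a linear model that has treatment as a factor. Name one of these as the primary between-arm test before unblinding. In simulation at the planning values, Student and Welch have nearly the same power (0.814 and 0.812). If Mann-Whitney is kept, either state the switching rule in advance or report it as a sensitivity analysis.

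The cost is one sentence of analysis wording. The correction does not itself alter the planned 26 participants, the data collected or anything done to patients.
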